1.2. Specific Aims

Aim1. To compare the two study conditions in terms of: (a) XR-NTX treatment adherence; (b) opioid use; (c) criminal activity; (d) re-arrest; (e) re-incarceration; and (f) HIV risk-behaviors (i. needle use; and ii. risky sexual behaviors).

Aim 2. To determine if the number of months of post-release XR-NTX treatment is related to outcomes (a)-(f), and if so, is there a point at which XR-NTX v. Non-XR-NTX equilibrates. Such a finding could be potentially important because it would be informative about the needed length of XR-NTX treatment.

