3.0. INNOVATION

The proposed study is innovative because it would be the first randomized controlled trial (RCT) in the US assessing effectiveness of receiving XR-NTX using medical mobile treatment compared to XR-NTX at an opioid treatment program. The public health impact of the proposed study will be highly significant and far-reaching because most individuals with OUDs do not receive treatment while incarcerated, thereby substantially raising their likelihood of re-addiction, overdose death, HIV/AIDS infection, and re-incarceration following release. Furthermore, many individuals in the criminal justice system drop out of treatment; therefore, offering opportunities to improve adherence by attempting to: 1) expand capacity; and 2) implement access by providing treatment at their place of residence may positively impact outcomes. The proposed study is significant as to our knowledge it would be the first RCT with long-acting naltrexone in a prison population. While other investigations have reported that naltrexone is effective among parolees and probationers and pilot studies have found that it is feasible with prison inmates, the present study will focus on whether the addition of mobile XR-NTX treatment will increase adherence and thus efficacy of the medication. Finally, the importance of finding a point of equilibration will provide evidence of how many monthly XR-NTX injections will be needed. More importantly, there is a continuing need for RCTs to further examine the efficacy and effectiveness of opioid maintenance therapies within specific incarcerated populations such as prisoners because different criminal justice populations could respond to treatment differently and we could adapt treatment to work better for specific populations.⁸²

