4.2. Design Considerations

We considered XR-NTX vs. treatment as usual but it was felt strongly that it would not be ethical to deny services to participants during this crucial transition period from prison to community. We also considered XR-NTX vs. placebo but still were of the opinion of denying newly released prisoners access to an intervention was not ethical. While the methods of this particular design are very strong, the ethics of providing no treatment to newly released inmates can be called into question. Furthermore, although we do not know for pre-release prisoners, past research suggests that XR-NTX is efficacious for probationers. Therefore, it would be unethical to *withhold what we would assume to be an efficacious treatment from some participants. Moreover, our interest was not in whether XR-NTX worked in this population, but to address the unanswered question of whether mobile medical services (XR-NTX) increased medication compliance, thereby reducing opioid use, HIV risk behaviors, and re-arrest, and re-incarceration. *While we understand a control group that did not receive XR-NTX might be considered a potent comparator, we chose XR-NTX without a mobile component as the control group for two reasons: (a) it was the 'obvious' comparison group to our XR-NTX mobile intervention, because we would be able to determine the added benefit of mobile treatment above and beyond XR-NTX alone; (b) Other control groups would not be feasible [methadone or buprenorphine, due to medication regulations, daily dosing, need for increased staffing, and problem with diversion; or unethical (no treatment)].*

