5.9. Study Aims, Hypothesis, Rationale

5.9.1. Aims. The proposed study has two specific aims: **Aim 1.** To compare the two study conditions in terms of: a) XR-NTX treatment adherence; b) opioid use; c) criminal activity; d) re-arrest; e) re-incarceration; and f) HIV risk-behaviors (i. needle use; ii. risky sexual behaviors). **Aim 2.** To determine if the number of months of post-release XR-NTX treatment is related to outcome (a-f above), and if so, is there a point at which XR-NTX v. Non-XR-NTX equilibrates.

5.9.2. Hypothesis. Based on data from the research team's current studies (see above), It is anticipated that the XR-NTX+MMTx condition will have superior outcomes compared to the XR-NTX+OTx condition in terms of outcomes (a)-(f).

5.9.3. Rationale. We are not aware of RCTs using mobile medical treatment for the provision of XR-NTX. However, based on studies utilizing mobile treatment for HIV services, and methadone, which increased access, engagement, and retention, we believe the provision of medical treatment, provided at a participant's place of residence, is expected to yield better adherence, subsequently, improving outcomes mentioned above. If we find a point of equilibration it will tell us how many months we will need to provide mobile treatment (XR-NTX) and at what point it impacts on outcomes-significant given the cost of the medication. It is difficult to provide firm conjectures on this latter question given the lack of research in this area.

Figure 2: Data Collection Schedule

Measures	Source	Interval	Operational Definition
Aim 1: Outcomes (a)-(f)			
a. XR-NTX adherence	Clinic records	B, 1-6	• # of injections due/completed
b. opioid use	ASI/TLFB/UDS	B, 1-6, 7, 12	• days of opioid use • positive opioid urine drug screen
c. criminal activity	ASI/TLFB	B, 1-6, 7,12	• days of crime
d. re-arrest	Official records	12	• time to re-arrest
e. re-incarceration	Official records	12	• time to re-incarceration
f. HIV risk behaviors	RAB/TLFB	B, 1-6, 7,12	• scored 0-22 (higher risk) • scored 0-18 (higher risk)
i. needle use			
ii. risky sex behaviors			
Aim 2: Outcomes (a)-(f)			
(a)-(f) equilibrates	Above	1-6,12	Time to relapse
Supplementary			
other treatment	ASI	B, 1-6, 7, 12	• Days in other treatment
opioid overdose	OOS	B, 1-6, 7, 12	• # of times overdosed
opioid craving	VAS	B, 1-6, 7, 12	• 0-100 (higher cravings)
Quality of Life	QOL	B, 1-6, 7, 12	

Figure 3: Biometric Measures

Measures	Data Collection Point						

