6.4. Explanatory Variables. The predictor variables in all statistical models can be categorized as either Treatment Variables, Covariates, or Control Variables. (From a statistical viewpoint, this categorization is arbitrary and is utilized here simply for ease of presentation.)

Treatment Variables. There will be a single treatment variable: Treatment Condition (XR-NTX-MMTx v. XR-NTX+OTx).

6.4.1. Covariates. Three additional predictor variables – Age, Gender, and age of onset of criminal activity – will be included as “main effects” in all analyses. These “main effects” test for the unique contribution of each of these variables in predicting outcome, above and beyond the effects of Treatment Condition. Each of these variables, as well as its respective interaction with Treatment Condition, will be included as a predictor in order to examine for potential differences in treatment outcome as a function of each covariate, and whether any of these three covariates moderate treatment efficacy.

6.4.2. Control Variables. Finally, because participants may know one another through contact at their respective prison, it is possible that participants' responses within a given prison will not be entirely independent of each other. This potential lack of independence must be controlled for by including Prison nested within Treatment Condition and Participants nested within Prison nested with Treatment Condition as random factors. [Although neither of these two effects represents a substantive effect of interest, both must be included in order to produce unbiased estimates and tests of significance for Treatment Condition.]

6.4.3. Time. Finally, the “repeated factor” in the statistical analysis of all outcome variables measured repeatedly will be assessment Time point, which will allow for the evaluation of both *differential course and impact* of the interventions as a function of the “between-subjects” Treatment Condition factor. (For information regarding which outcome variables are measured at what assessment time points, see **Figure 2**, above.)

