9.5. Participation of Prisoners

The proposed study involves research on prisoners and therefore is subject to DHHS regulations that provide additional protections for research involving prisoners as research participants. In keeping with their vulnerable status as prisoners, all study participants will receive treatment prior to release (XR-NTX) in prison and in the community and information on how to access various treatment resources in the community. XR-NTX is approved by the FDA for the prevention of relapse to opioid dependence. Both treatment conditions will be receiving study medication. Thus, the study will not employ a “no treatment” control condition, inasmuch as all participants will receive an active substance use treatment (i.e., XR-NTX).

We are sensitive to the possibility that, given the limited financial resources of many prisoners at this point in time, providing cash compensation at baseline could unduly influence inmates to participate in this intervention study. Furthermore, we consider that the treatment that participants receive is ample compensation for the time that they devote to research procedures at baseline. Therefore, no cash compensation will be provided for baseline assessments. Cash compensation will be provided for follow-up interviews conducted following release in recognition of participants' contribution of their time and efforts to the research.

We are also sensitive to ensuring that participants are not being coerced to enroll in the study. Thus, the process of participant enrollment (including participant screening, informed consent, baseline assessment, and medical examinations) will take place without correctional staff present, in private discussions with the research and medical staff of the study. Furthermore, as mentioned above, because of the possibility of coercion when working with prisoners, the study RAs will emphasize that the decision to participate or not will not affect the prisoner's status, privileges, or release date.

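### Section 5.9.3 draws a duration for mobile treatment from an on-drug versus off-drug contrast that does not compare mobile with clinic delivery

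*Combined protocol and SAP*

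**What the plan says.** Aim 2 (section 1.2, repeated in 4.1 and 5.9.1) has two steps. The first is "To determine if the number of months of post-release XR-NTX treatment is related to outcomes (a)-(f"). The second, taken only if such a relation is found, asks "is there a point at which XR-NTX v. Non-XR-NTX equilibrates".

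The documents state three times what the answer would be used for:

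- Section 1.2: "it would be informative about the needed length of XR-NTX treatment".
- Section 3.0: "the importance of finding a point of equilibration will provide evidence of how many monthly XR-NTX injections will be needed".
- Section 5.9.3: "If we find a point of equilibration it will tell us how many months we will need to provide mobile treatment (XR-NTX").

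The first two concern the drug. The third concerns mobile delivery.

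On design, section 9.5 says "Both treatment conditions will be receiving study medication", and section 4.2 says "our interest was not in whether XR-NTX worked in this population"; the stated interest there is the added benefit of mobile services. Section 6.4 says "There will be a single treatment variable: Treatment Condition (XR-NTX-MMTx v. XR-NTX+OTx"). Section 6 gives no Aim 2 model, no term crossing arm with months received, and no criterion for equilibration. The Aim 2 row of Figure 2 gives only time to relapse.

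**The concern.** Mobile versus clinic delivery is the factor this trial randomises. How long mobile delivery is needed is a question about that factor, and only a comparison of the two arms can answer it. The equilibration point is instead a feature of the relation between receiving XR-NTX and outcome. It can exist, and fall at the same month, whether or not the place of injection matters.

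At stake is a service recommendation. A report that followed 5.9.3 literally could state a required number of months of home delivery beside an Aim 1 result showing no benefit of home delivery.

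This is separate from confounding of months received by prognosis. Even a perfectly unconfounded on/off contrast would show how long the drug is needed, not where it must be given.

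**Working it through.** **1. The contrast, written out.** Let A be the randomised arm, M(t) be 1 if the participant is on XR-NTX at month t and 0 if not, and Y(t) the outcome. A model with the arm as a main effect is

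logit P(Y(t)=1) = b0(t) + bA·A + bM(t)·M(t).

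The equilibration point is the first t at which bM(t) reaches zero, or falls within some margin of it. That definition does not involve bA. Setting bA = 0 and giving both arms the same distribution of M leaves bM(t), and hence the point, unchanged. There is no randomised Non-XR-NTX arm, so M = 0 can only mean people in either arm who stopped or missed injections.

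**2. The nearest stated figure.** The documents give no power or precision for Aim 2. Section 6.7 gives f² = .037 for power .80 on the randomised main effect, with N = 216 and α = .05. Check: noncentral F with 1 and 214 df, noncentrality .037 × 216 = 7.99, gives power .8035. The figure reproduces, and it refers to the randomised contrast, not the equilibration contrast.

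**3. The investigators' own pilot (section 2.7.3).** All community injections were given at the clinic. Completers versus non-completers were 0% v 63% opioid-positive, p = .003. The split 0/10 v 10/16 fits those percentages (10/16 = 62.5%; the denominator 16 is inferred) and gives Fisher p = .0026. A months-received contrast was thus strongly significant with no mobile delivery at all.

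**4. Simulation with a simple equilibration rule.**

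From the documents:
- 216 participants (108 per arm).
- Community injections 1 to 6 received by 21, 18, 13, 11, 10 and 10 of 27 (2.7.3).
- Urine positive 26% on drug and 44% off drug, taken as 100 − 74 and 100 − 56 from the XR-NTX v usual-treatment result in 2.7.2.

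Assumed, not in the documents:
- Equilibration is the first month with an off-minus-on difference under 5 points.
- The off-drug rate either falls to 26% from month 4 in both arms, or stays at 44%.
- A mobile effect, where present, is a 20-point gain in retention.

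| Off-drug rate | No mobile effect: month named | 20-point retention gain: month named |
|---|---|---|
| Converges at month 4 | 99% (month 4 in 72%) | 99% (month 4 in 67%) |
| Never converges | 16% | 22% |

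(4,000 trials per cell.) The rows differ greatly and the columns little. The naming rate is driven by the assumed on/off course.

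**5. Simulation with a different rule and exactly zero mobile effect.** 120 per arm, pilot retention in both arms, 2,000 trials per setting. Assumed: a logistic outcome; a months effect of either 0.4 log-odds per month up to month 4 or zero; and a prognosis that may correlate with staying on. A month is sought only if months received relate to outcome at p < .05.

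| Setting | Months–outcome relation significant | Arm difference significant |
|---|---|---|
| Real months effect | 99–100% | 5% |
| No months effect, prognosis correlated .3 / .5 / .7 with staying on | 27 / 63 / 91% | 5% |
| Neither | 2% | 4% |

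Counting only a named month of 1 or later, the first row becomes 89–100% and the second 11 / 32 / 66%. Adding the arm as a main effect moves the months slope from −0.225 to −0.226 and leaves the proportion significant at 98.9%.

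**The case against.** The strongest reply is that one loose word is being read as a decision rule. The sentence stands in a rationale, not in section 6. It is conditional on finding a point, and the section goes on to say that firm conjecture is difficult. The drug name follows in parentheses, and the sentence ends on the cost of the medication, which is an argument about drug duration. Sections 1.2 and 3.0 are also about the drug. This may well be what was meant. If so, the remedy is to delete the word; left in place, the sentence still states a conclusion that the contrast cannot support. The closing hedge concerns what the answer will be, not whether this contrast can supply one for mobile delivery.

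A second reply is that the randomised question is already analysed as randomised: Aim 1 compares the arms, 6.4.3 and 6.7 plan and power Treatment Condition by Time, and 6.1 promises confidence intervals. That stands, and it limits the harm, because a null mobile effect would show in Aim 1. But no passage makes the 5.9.3 conclusion wait for that result.

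A reader might infer that the plan will nearly always name a duration for mobile treatment. The documents do not support this. The 99% in step 4 comes from convergence at month 4, which was assumed and has no source in the documents; without it the figure is 16% to 22%. If months received are unrelated to outcome, step 5 gives about 2%.

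A reader might also infer that the randomised arm is left out of the Aim 2 model. Section 6.4 makes Treatment Condition the treatment variable, so it may well be included. As a main effect it simply does not change the on/off contrast.

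**Conclusion.** Wrong as written, for one conclusion of a secondary aim. The equilibration point is defined on drug received, across both arms, so it cannot say how many months of mobile delivery are needed. Section 5.9.3 also conflicts with 1.2 and 3.0 on what the point means. The plan *can* report a duration for mobile treatment when the arms do not differ; it is not certain to.

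This conclusion follows from the definitions and needs no simulation. The size does need assumptions: depending on the course of off-drug outcomes, on how prognosis relates to staying on, and on the equilibration rule, the share of trials with no mobile effect that name a month runs from about 2% to about 100%. The direction holds under both rules tried: a month is named, or not, largely without regard to whether mobile delivery works. Randomisation, data collection, sample size and Aim 1 are unaffected.

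**What to change.** 1. In 5.9.3, delete the word mobile from the sentence on equilibration, so that Aim 2 speaks only about XR-NTX exposure, in line with 1.2 and 3.0.
2. If a statement on how long mobile delivery matters is wanted, base it on the randomised contrast: tabulate the XR-NTX+MMTx minus XR-NTX-OTx difference at each of months 1 to 6, with confidence intervals, for adherence and for opioid use, from the Treatment Condition by Time models already planned.
3. State that no duration for mobile delivery will be given on an outcome unless the randomised arms differ on it. In step 5, with no mobile effect, such a condition would be met in about 4–5% of trials per outcome, or 2–3% in favour of mobile delivery.

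The cost is a change of wording and one table. Figure 2 already schedules both outcomes at months 1 to 6, so no new data, visits or participants are needed. The downside is a narrower Aim 2 claim.

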6.0. Statistical Analyses

6.1. Guiding Principle. Although the description of the statistical approach that follows is more in line with the language associated with a ‘traditional’ superiority trial, we endorse the “sensible formulation of the significance test” proposed by Jones and Tukey.⁹⁷ These authors outline an approach to significance testing that focuses not on the rejection of a null hypothesis, but on determining whether the data favor a determination of superiority or inferiority. As part of their approach, they suggest reporting not only a test statistic and its associated probability value but also a confidence interval and an effect size related to the determination of any difference. It would be our intention in reporting our results to adhere to Jones and Tukey’s suggestions.

6.2. Intent-to-Treat Approach. All analyses will be conducted on available study-related data from all participants, regardless of whether or when they drop out of treatment; i.e., the intent-to-treat population is all persons consented and randomized to the study.

6.3. Outcome Measures. Except for criminal justice records, collected at study conclusion, outcome data will have been collected monthly during the project: at baseline (study entry), and at 1, 2, 3, 4, 5, 6, 7, and 12 months following release from prison (see **Figure 2**, above). The resulting dependent variables will be of three distinct types: 1) continuous random variables (e.g., RAB scale scores), assumed to follow a normal distribution; 2) discrete random variables (e.g., number of days of criminal activity), assumed to follow a Poisson distribution; and, 3) dichotomous variables (e.g., treatment adherence, urine drug screening results), assumed to follow a binomial distribution. [All distributional assumptions will be evaluated prior to the conduct of all analyses, and if such assumptions are not met, assumptions will be modified and statistical methods chosen accordingly, and/or outcome measures transformed appropriately. For example, it may be necessary to allow for under- or over-dispersion in the logistic and Poisson regression analyses, or use zero-inflated Poisson or negative binomial models rather than a Poisson model for the count variables.]

6.4. Explanatory Variables. The predictor variables in all statistical models can be categorized as either Treatment Variables, Covariates, or Control Variables. (From a statistical viewpoint, this categorization is arbitrary and is utilized here simply for ease of presentation.)

Treatment Variables. There will be a single treatment variable: Treatment Condition (XR-NTX-MMTx v. XR-NTX+OTx).

6.4.1. Covariates. Three additional predictor variables – Age, Gender, and age of onset of criminal activity – will be included as “main effects” in all analyses. These “main effects” test for the unique contribution of each of these variables in predicting outcome, above and beyond the effects of Treatment Condition. Each of these variables, as well as its respective interaction with Treatment Condition, will be included as a predictor in order to examine for potential differences in treatment outcome as a function of each covariate, and whether any of these three covariates moderate treatment efficacy.

6.4.2. Control Variables. Finally, because participants may know one another through contact at their respective prison, it is possible that participants' responses within a given prison will not be entirely independent of each other. This potential lack of independence must be controlled for by including Prison nested within Treatment Condition and Participants nested within Prison nested with Treatment Condition as random factors. [Although neither of these two effects represents a substantive effect of interest, both must be included in order to produce unbiased estimates and tests of significance for Treatment Condition.]

6.4.3. Time. Finally, the “repeated factor” in the statistical analysis of all outcome variables measured repeatedly will be assessment Time point, which will allow for the evaluation of both *differential course and impact* of the interventions as a function of the “between-subjects” Treatment Condition factor. (For information regarding which outcome variables are measured at what assessment time points, see **Figure 2**, above.)

6.5. Statistical Method. A Generalized Linear Mixed Model (GLiMM) will be used to conduct all analyses. [For the case in which the outcome is measured only at the end of study participation (e.g., reincarceration), GLiMM reduces to the generalized linear model (GLiM).] It is not necessary that the within-subjects set of observations either be complete or collected at the same points in time for GLiMM models. GLiMM will make use of all available data, and hence, is an ideal statistical procedure for “intent-to-treat” approaches to data analysis, as occurs in the study proposed herein.

6.6. Missing Data. GLiMM is quite flexible in the presence of missing data for outcome variables, and it is not necessary for participants to have complete outcome data to be included in GLiMM analyses; in general, GLiMM will make use of all available data, and hence, is an ideal statistical procedure for intent-to-treat approaches to data analysis in the case of ignorable missingness (ie, MCAR and MAR). However, a pattern mixture model approach⁹⁸ to modeling the missingness as part of statistical estimation will be utilized if there are a sufficient number of identifiable patterns to the missingness. The potential impact of missingness and the operation of the missing data mechanism(s) will be examined from a multiple imputation perspective.^{99,100}

6.7. Power. Stroup¹⁰¹ (also see Littell et al.¹⁰²) has outlined a four-step procedure to estimate power for general linear mixed models, which can also be applied to generalized linear mixed models as occur in the proposed study. This procedure was implemented in the current case. For each of the number of Times outcomes were measured (4, 5, 6, 7, or 9), three datasets for each hypothesis were created, assuming the dependent variable was continuous and normally distributed, discrete and Poisson distributed, or dichotomous and binomially distributed. For the normally distributed case, the only non-null effect in the model was the hypothesized effect of interest, with the XR-NTX-OTx condition mean set at 1 at Time 1, decreasing by .1 at each subsequent Time point, while the XR-NTX+MMTx condition means were set at 1 at Time 1, and then adjusted to reflect “small”¹⁰³ mean differences (.2 of the standard deviation at subsequent Time points) consistent with the hypothesis of interest. [Time was not included in the estimation of power for the criminal justice outcomes because these outcomes are measured only at 12-month post-baseline assessment.] Similar specifications were made for the datasets with outcomes following the Poisson and binomial distributions. Finally, observations were dropped from the data consistent with the expected loss of approximately 10% of participants at the 12-month assessment (see **Participant Attrition**, above). Hence, power was estimated for a design in which the effects were unbalanced in a manner similar to what was expected to occur in the proposed research. Therefore, simulations were conducted under what might be considered “worst-case scenarios.” Power was then estimated for three different covariance structures (compound symmetric heterogeneous, first-order autoregressive heterogeneous, and unstructured) of the observations over Time. [Covariance structures can be specified for GLiMM models independent of the location (e.g., mean) structure, so it was only necessary to create a single dataset for the three cases.] Assuming a sample size of 240 and $\alpha=.05$, the resulting power values ($1 - \beta$) for the Treatment Condition X Time effect varying between .81 and .85 in the simulations. From a more rudimentary and slightly less accurate perspective, assuming the primary outcome measures follow a normal distribution rather than binomial or Poisson distributions, power calculations based on the set correlation method¹⁰⁴ can be used to calculate effect sizes for desired power, including under the extremely conservative assumption that no other effect in the model is significant (with the resulting effect size estimates likely to be slight underestimates). In this case, assuming $\alpha=.05$ and $N=216$ due to attrition (see **Participant Attrition**, above) in order to remain conservative, an effect size of $f^2=.037$ in the population associated with a Treatment Condition main effect for statistical models in which there is no Time effect (e.g., reincarceration) and effect sizes ranging from a minimum $f^2=.046$ to a maximum $f^2=.072$ for the Treatment Condition X Time effects associated with the 4, 5, 6, 7, or 9 Time points for statistical models in which there is a Time effect, would yield a power of .8 for the respective effect. These effect sizes fall toward the “small-to-medium” range, with $f^2=.02$ considered a “small” effect and $f^2 = .15$ a “medium” effect.¹⁰³ In other words, and imprecisely, under the assumption that the effect in the population was $\geq .037$ or $\geq .072$, for the Treatment Condition and Treatment Condition X Time effects, respectively, there is an 80% chance of concluding that effect is significant if α is set to .05 and 216 participants are assessed at 12-month follow-up. *Power calculations do not utilize any estimates of treatment efficacy from prior studies. This latter approach to power analysis, although once popular, is often quite limited, as is the case for the proposed study, in that prior studies may have examined populations that are not comparable to the population in the proposed study and/or do not include the same experimental or control conditions, and in all cases, the effect sizes reported in prior studies are generally subject to wide fluctuation due to sampling variability.*¹⁰⁵ Power was calculated to detect a stated effect size, as detailed in the proposal, an approach consonant with more recent writings regarding power analysis.

6.8. Supplementary Analyses. We will tabulate (and test for treatment condition differences) for the relative frequency of each adverse event (AE) in each condition, where the examination is based on the proportion of

individuals who experience the AE, and the number of that AE reported. In addition, we will tabulate and test for treatment condition differences) for the relative frequency of opioid overdoses in each condition, where the examination is based on the proportion of individuals who report overdoses during the 12-months post-release. We will also calculate mean scores of cravings at each follow-up.

6.9. Additional Process Data *We will collect three additional process variables: (1) data on housing stability at each follow-up visit that will utilize a checklist to describe the participant's place of residence and the level of stability; (2) data on the distance travelled from place of residence to Glenwood Life Counseling Center (GLC) for participants randomized to TAU; and (3) data on the number of counseling sessions received during the course of the study (this will account for any community counseling received during treatment).*

6.10. Follow-up Analyses. *Follow-up analyses will include select covariates in the model, with a focus on the covariate X BI Intervention Condition (X Time, if an outcome is measured repeatedly). These follow-up analyses can be viewed as either sensitivity analyses or as subgroup analyses^{106,107} intended to map the population(s) for which the intervention is maximally useful and/or examine the robustness of the findings under uncertainty in the model. Possible covariates include: (1) crime severity, (2) opioid severity, (3) housing stability, (4) distance travelled from place of residence to treatment clinic; and (5) number of counseling sessions received.*

